## 13.6 Publications and Clinical Study Report

## 13.6.1 Publication of Study Results

Vertex is committed to reporting the design and results of all clinical studies in a complete, accurate, balanced, transparent, and timely manner, consistent with Good Publication Practices (GPP3).

**Publication Planning**: Vertex staff along with the lead principal investigators (PIs), the steering committee (SC), and/or the publication committee (PC) will work together to develop a publication plan.

**Authorship**: Authorship of publications will be determined based on the Recommendations for Conduct, Reporting, Editing, and Publication of Scholarly Work in Medical Journals, which states that authorship should be based on the following 4 criteria:

- 1. Substantial contributions to conception and design, acquisition of data, or analysis and interpretation of data;
- 2. Drafting of the article or revising it critically for important intellectual content;
- 3. Final approval of the version to be published; and
- 4. Agreement to be accountable for all aspects of the work in ensuring that questions related to the accuracy or integrity of any part of the work are appropriately investigated and resolved.

All authors must meet conditions 1, 2, 3, and 4. All persons designated as authors should qualify for authorship, and all those who qualify should be listed. Contributions such as medical writing, enrollment of subjects, acquisition of funding, collection of data, or general supervision of the research group, alone, do not justify authorship.

**Contributors**: Contributors who meet fewer than all 4 of International Committee of Medical Journal Editors (ICMJE) criteria for authorship will not be listed as authors, but their contribution will be acknowledged and specified either as a group (e.g., "study investigators") or individually (e.g., "served as scientific advisor").

**Publication Review**: As required by a separate clinical study agreement, Vertex must have the opportunity to review all publications, including any manuscripts, abstracts, oral/slide

presentations, and book chapters regarding this study before submission to congresses or journals for consideration.

# 13.6.2 Clinical Study Report

A CSR, written in accordance with the ICH E3 Guideline, will be submitted in accordance with local regulations.

2 LIST OF ABBREVIATIONS

Abbreviation	Definition
AE	adverse event
AESI	adverse event of special interest
BMI	body mass index
CDC	Centers for Disease Control and Prevention
CF	cystic fibrosis
CFTR	CF transmembrane conductance regulator protein
CI	confidence interval
CMQ	Custom MedDRA Queries
CRF	case report form
DBP	diastolic blood pressure
DMC	data monitoring committee
ECG	electrocardiogram
eCRF	electronic CRF
ETT	early termination of treatment
F508del	CFTR gene mutation with an in-frame deletion of a phenylalanine
1 300dC1	codon corresponding to position 508 of the wild-type protein
FAS	Full Analysis Set
FDA	Food and Drug Administration
FE-1	fecal elastase-1
HR	heart rate
ICF	informed consent form
IPD	important protocol deviation
IRT	immunoreactive trypsin and trypsinogen
IVA	Ivacaftor
LFT	liver function test
LLN	lower limit of normal
LUM	Lumacaftor
MedDRA	Medical Dictionary for Regulatory Activities
NHLBI	National Heart, Lung, and Blood Institute
OE	ophthalmological examination
PD	pharmacodynamics(s)
PE	physical examination
PR	PR interval
PT	preferred term
PY	patient-year: a patient with 48 weeks of treatment-emergent duration
q12h	every 12 hours
QRS	the portion of an ECG comprising the Q, R, and S waves, together
C -3-2	representing ventricular depolarization
QT	QT interval
QTc	QT interval corrected
RR	interval from the onset of 1 QRS complex to the next
SAE	serious adverse event
SAP	statistical analysis plan
SBP	systolic blood pressure
77 DI	

SD standard deviation SE standard error SFU safety follow-up

SI units (International System of Units)

SOC system organ class TE treatment-emergent

TEAE treatment-emergent adverse event

TFLs tables, figures, and listings ULN upper limit of normal

US United States

WHO World Health Organization

WHODrug World Health Organization Drug Dictionary

3 MODIFICATIONS

3.1 Modifications to the Approved Clinical Study Protocol

Typographical and administrative changes were made to improve the clarity of the document.

3.2 Modifications to the Approved Statistical Analysis Plan

This is the first version of the SAP (Methods) for the final analysis.

3.3 Modifications to the Approved IDMC Charter

None.

4 INTRODUCTION

Study VX19-809-124 is a Phase 3, open-label, and rollover study to evaluate the long-term safety and tolerability of Lumacaftor/Ivacaftor (LUM/IVA) treatment in subjects with cystic fibrosis (CF) who are homozygous for *F508del* and 12 to <24 months of age at treatment initiation.

This statistical analysis plan (SAP) is for the final analysis of Study VX19-809-124 (Study 124) data and is based on the:

- approved clinical study protocol, dated 12 February 2021, Version 2.0
- approved electronic case report form (eCRF), dated 10 April 2021, Version 6.0

This SAP (Methods) documents the planned statistical methods and data presentations of the final analysis for Study 124. It also documents additional analyses not prespecified in the protocol, but necessary for the scientific understanding of the drug entity.

The Vertex Biometrics Department or designee will perform the statistical analysis described in this document; SAS (Version 9.4 or higher) will be used to generate all statistical outputs (tables, figures, listings, and datasets).

This SAP will be finalized and approved prior to the data cut for the final analysis of Study 124. Any revisions to the approved SAP will be documented and approved in an amendment to the SAP.

5 STUDY OBJECTIVES

5.1 Primary Objective

To evaluate the safety and tolerability of long-term LUM/IVA treatment in subjects with CF, who are homozygous for *F508del* and 12 to <24 months of age at treatment initiation.

5.2 Secondary Objective

To evaluate the pharmacodynamics (PD) of long-term LUM/IVA treatment in subjects with CF, who are homozygous for *F508del* and 12 to <24 months of age at treatment initiation.

5.3 Other Objectives

Not Applicable.

6 STUDY ENDPOINTS

6.1 Primary Endpoint

Safety and tolerability assessments based on adverse events (AEs), clinical laboratory (serum chemistry and hematology), standard 12-lead electrocardiograms (ECGs), vital signs, pulse oximetry, and ophthalmological examinations (OEs).

6.2 Secondary Endpoint

Absolute change from baseline in sweat chloride.

6.3 Exploratory Endpoints

Absolute change from baseline in the following growth parameters:

- Body mass index (BMI)-for-age z-score and BMI
- Weight-for-age z-score and weight

- Length/height-for-age z-score and length/height
- Weight-for-length z-score

Absolute change from baseline in the following markers of pancreatic function:

- Fecal elastase-1 (FE-1) levels
- Serum immunoreactive trypsin and trypsinogen (IRT) levels

Absolute change from baseline in fecal calprotectin, a marker of intestinal inflammation.

7 STUDY DESIGN

7.1 Overall Design

This is a Phase 3, multicenter, open-label study in subjects who are 12 to <24 months of age at initiation of LUM/IVA treatment (

Figure 7-1). The study will enroll approximately 50 subjects.

Rollover Subjects

Subjects who participated in parent study VX16-809-122 Part B (Study 122B) and meet all eligibility requirements can rollover into Study 124.

For rollover subjects at sites activated by the Study 122B Safety Follow-up (SFU) Visit, their Study 124 Day 1 Visit will be on the same day as their Study 122B SFU Visit; any Study 124 Day 1 assessments that are specified to be performed at the Study 122B SFU Visit will not need to be repeated.

If the Study 124 Day 1 Visit does not coincide with the Study 122B SFU Visit, and if Study 124 Day 1 is \leq 9 days after the Study 122B SFU Visit, the Study 124 Day 1 assessments will not need to be repeated. Otherwise, if Study 124 Day 1 is >9 days after the Study 122B SFU Visit, the subject will need to complete all Study 124 Day 1 assessments (except the OE if it was performed \leq 12 weeks before the Study 124 Day 1 Visit).

Rollover subjects may receive treatment for up to 120 weeks (24 weeks in Study 122B and 96 weeks in Study 124).

LUM/IVA-naïve Subjects

[figure not shown]
Subjects who did not participate in Study 122B and are 12 to <24 months of age at Study 124 Day 1 can enroll by age group if they meet Study 124 eligibility requirements:

- Subjects who are 18 to <24 months of age can enroll in Study 124 after a minimum of 10 subjects (aged 18 to <24 months) have enrolled in Study 122B and after an assessment of safety data from Study 122B through Week 12 for ≥5 subjects aged 18 to <24 months.
- Subjects who are 12 to <18 months of age can enroll in Study 124 after a minimum of 10 subjects (aged 12 to <18 months) have enrolled in Study 122B and after an assessment of safety data from Study 122B through Week 12 for ≥5 subjects aged 12 to <18 months.

Note: Subjects aged 18 to <24 months will start enrolling in Study 124 before any subjects 12 to <18 months of age can enroll as a result of the staggered timing from the Study 122 study design, which includes sequential age cohorts.

LUM/IVA-naïve subjects may receive treatment for up to 96 weeks in Study 124.

Figure 7-1 Schematic of Study 124 Design

IVA: ivacaftor; LUM: lumacaftor; OE: ophthalmological examination; q12h: every 12 hours; wks: weeks

- LUM/IVA-naïve subjects (by age group: 18 to <24 months and 12 to <18 months) will be able to enroll in Study 124 once minimum enrollment has been met in Study 122B (n = 10 subjects in each age group), and after an assessment of safety data from Study 122B through Week 12 for ≥5 subjects in each age group.
- b For rollover subjects, the Day 1 Visit should be the same day as the Safety Follow-up Visit in Study 122B.
- The Safety Follow-up Visit will not be required for subjects transitioning to commercial LUM/IVA.
- ^d For LUM/IVA-naïve subjects, doses will be determined by weight at screening.

7.2 Sample Size and Power

No formal sample size calculations have been performed for this study. The study will enroll approximately 50 subjects to provide data for the assessment of long-term safety in the target patient population, as requested by a regulatory agency.

7.3 Randomization

This is an open-label study with weight-based treatment dosing. Randomization is not required.

7.4 Blinding and Unblinding

This is an open-label study.

8 ANALYSIS SETS

The following analysis sets are defined. Enrolled subjects are those who signed consent/assent form and had an enrollment date in the database.

All Subjects Set: All subjects who are enrolled or dosed in Study 124. This analysis set will be used for individual subject data listings and disposition summary tables unless otherwise specified.

Safety Set: All subjects who are exposed to any amount of study drug in Study 124. This analysis set will be used for all safety analysis unless otherwise specified.

Full Analysis Set: All subjects who are enrolled and dosed in Study 124. This analysis set will be used for all analysis of PD and exploratory endpoints unless otherwise specified.

9 ANALYSIS PERIOD

The analysis periods are described below.

The **Treatment-emergent (TE) Period** will start on or after the first dose date of study drug in Study 124 to 18 days (inclusive) after the last dose date of study drug in Study 124 or up to the last day in Study 124, whichever occurs first.

10 STATISTICAL ANALYSIS

10.1 General Considerations

The Schedule of Assessments is provided in the CSP for Study 124. The precision standards for reporting safety and efficacy variables are provided in an internal Biometrics document that specifies the programming rules including the precision for derived variables.

All individual subject data will be presented in data listings based on the All Subjects Set.

Continuous variables will be summarized using the following descriptive summary statistics: number of subjects, mean, standard deviation (SD), standard error (SE), median, minimum value (min), and maximum value (max).

Categorical variables will be summarized using counts and percentages.

Baseline value will be defined as the most recent non-missing measurement (scheduled or unscheduled) collected on or before the first dose of LUM/IVA in Study 124.

For sweat chloride, values at each visit will be based on averaged measurements from left and right arms. For Rollover Subjects, baseline will be defined as the most recent non-missing measurement (scheduled or unscheduled) collected on or before the first dose of LUM/IVA in Study 124. For LUM/IVA-naïve Subjects, baseline will be defined as the average of the values at screening and the pretreatment measurement on Day 1 of Study 124. If only 1 pre-first dose measurement of sweat chloride is available, that measurement will be considered the baseline.

Change (Absolute Change) from baseline will be calculated as postbaseline value – baseline value.

Unscheduled visits will be included in the analysis as follows:

- In scheduled visit windows per specified visit windowing rules
- In the derivation of baseline measurements or last on-treatment visit
- In individual subject data listings, as appropriate
- In the derivation of max/min values and max/min change from baseline values

Visit windowing rules: Appendix defines the visit window mapping rules to derive the analysis visits for Study 124.

Repeated observations within the same visits window:

- For all PD parameters, if there are multiple measurements within a visit window, the record at the scheduled visit will be used. If there are no measurements at the scheduled visit, then 1) the record closest to the target day will be used; or 2) if there are multiple records with the same distance to the target day, the latest record will be used.
- For all safety parameters, if there are multiple measurements within a visit window, then 1) the record closest to the target day will be used; or 2) if there are multiple records with the same distance to the target day, the latest record will be used.
- If there are local lab results and central lab results at same visit point, then the central lab results will be used.

BMI, weight, and length will follow PD parameter visit window rules when evaluated as PD endpoints; they will follow safety parameter visit window rules when evaluated as safety endpoints. Their corresponding z-scores will be assigned analysis visit window rules the same as BMI, weight, and length, respectively.

For clinical laboratory, ECG and vital sign measurements collected on the date of the first dose of study drug, if it cannot be determined whether the measurement was taken before or after the first dose, scheduled measurements will be treated as pre-dose observations, and unscheduled measurements will be treated as post-dose observations.

If ETT visit happens on or after 10 days of last LUM/IVA dose and there are no SFU assessments collected, then ETT Visit will be mapped to SFU Visit.

Incomplete/missing data will not be imputed, unless specified otherwise.

Outliers: No formal statistical analyses will be performed to detect or remedy the presence of statistical outliers, unless specified otherwise.

Multiplicity: No multiplicity adjustment will be performed, and there is no hypothesis testing.

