### 8.1 Rollover Subjects

### 8.1.1 Inclusion Criteria

- 1. Subject's legally appointed and authorized representative (e.g., parent or legal guardian) will sign and date an informed consent form (ICF).
- 2. Completed the 24-week Treatment Period and the Safety Follow-up Visit in Study 122B.

Note: Subjects who had study drug interruptions during Study 122B are eligible for Study 124 if they completed the study visits in the Treatment Period and the Safety Follow-up Visit. Subjects who had a study drug interruption at Week 24 of Study 122B or subjects who resumed study drug in Study 122B after a study drug interruption due to elevated transaminases but who did not complete at least 4 weeks of rechallenge with study drug (due

- to <4 weeks remaining in the Study 122B Treatment Period) must meet eligibility criteria and receive approval from the Vertex medical monitor.
- 3. Subject's legally appointed and authorized representative (e.g., parent or legal guardian) are willing to have the subject remain on a stable CF medication regimen through the Safety Follow-up Visit.

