#### 8.2 LUM/IVA-naïve Subjects

#### 8.2.1 Inclusion Criteria

- 1. Subject's legally appointed and authorized representative (e.g., parent or legal guardian) will sign and date an informed consent form (ICF).
- 2. As deemed by the investigator, the subject's legally appointed and authorized representative (e.g., parent or legal guardian) must be able to understand protocol requirements, restrictions, and instructions. The subject's legally appointed and authorized representative should be able to ensure that the subject will comply with, and is likely to complete, the study as planned.
- 3. Subjects (male and female) will be 12 to <24 months of age on Day 1.
- 4. Weight at screening must be within the weight limits as defined for the study drug dose levels (see Section 9.6) or according to the dosing guidelines identified in the "Justification for Dose Selection" memorandum effective at the time a subject is screened.

- 5. Subjects with confirmed diagnosis of CF at screening. CF is defined as:
  - 2 CF-causing mutations (all as documented in the subject's medical record)
    - O Subjects must be homozygous for *F508del* (genotype to be confirmed at screening): If a genotype test has been performed previously and is documented in the subject's medical record, the subject is not required to be tested for *CFTR* genotype at screening, but the subject's eligibility must be approved by the Vertex medical monitor. If a historic genotype result is not available at screening or if the historic genotype result is not approved by the Vertex medical monitor, the subject will be tested for *CFTR* genotype at screening, and the results must be reviewed before the first dose. Note: Newborn screening genotype results are not sufficient for eligibility.

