#### 8.2.2 Exclusion Criteria

- 1. History of any comorbidity reviewed at screening that, in the opinion of the investigator, might confound the results of the study or pose an additional risk in administering LUM/IVA to the subject. For example, a history of cirrhosis with portal hypertension.
- 2. Any clinically significant laboratory abnormalities at screening that would interfere with the study assessments or pose an undue risk for the subject (as deemed by the investigator).
- 3. Any of the following abnormal laboratory values at screening:
  - Hemoglobin < 9.5 g/dL
  - Alanine aminotransferase (ALT), aspartate aminotransferase (AST), or total bilirubin >2 × upper limit of normal (ULN)
  - Chronic kidney disease of Stage 3 (estimated glomerular filtration rate [eGFR] <60 mL/min/1.73 m^2 calculated by the Bedside Schwartz equation) based on the normal range for eGFR in this age group (62 to 191)
- 4. An acute upper or lower respiratory infection, pulmonary exacerbation (PEx), or changes in therapy (including antibiotics) for pulmonary disease within 28 days before Day 1 (first dose of LUM/IVA).

- 5. A standard 12-lead ECG demonstrating QTc >450 msec at screening. If QTc exceeds 450 msec at the Screening Visit, the ECG should be repeated 2 more times during the Screening Period, and the average of the 3 QTc values should be used to determine the subject's eligibility.
- 6. History of solid organ or hematological transplantation.
- 7. Ongoing or prior participation in an investigational drug study (including studies investigating LUM and/or IVA) within 30 days of screening.
  - A washout period of 5 terminal half-lives of the previous investigational study drug, or 30 days, whichever is longer, must elapse before the Screening Visit.
  - The duration of the elapsed time may be longer if required by local regulations.

Note: Ongoing participation in a noninterventional study (including observational studies) is permitted.

[figure not shown]
- 8. Use of restricted medication or food within specified duration before the first dose of LUM/IVA as defined in Section 9.4.
- 9. An adequate slit-lamp examination could not be conducted at the Screening OE.

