#### 9 STUDY IMPLEMENTATION

### 9.1 Study Design

This is a Phase 3, multicenter, open-label study in subjects who are 12 to <24 months of age at initiation of LUM/IVA treatment (Figure 9-1). The study will enroll approximately 50 subjects.

Figure 9-1 Study 124 Design

IVA: ivacaftor; LUM: lumacaftor; OE: ophthalmological examination; q12h: every 12 hours; wks: weeks

- a LUM/IVA naïve subjects (by age group: 18 to <24 months and 12 to <18 months) will be able to enroll in Study 124 once minimum enrollment has been met for Study 122B (n = 10 subjects in each age group) and after an assessment of safety data from Study 122B through Week 12 for ≥5 subjects in each age group.
- b For Rollover Subjects, the Day 1 Visit should be the same day as the Safety Follow-up Visit in Study 122B.
- The Safety Follow-up Visit will not be required for subjects transitioning to commercial LUM/IVA (Section 9.1.3).
- For LUM/IVA-naïve subjects, doses will be determined by weight at screening.

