### Timing of Day 1 Visit

For rollover subjects at sites activated by the Study 122B Safety Follow-up Visit, their Study 124 Day 1 Visit will be on the **same day** as their Study 122B Safety Follow-up Visit. Any Study 124 Day 1 assessments that are specified to be performed at the Study 122B Safety Follow-up Visit do not need to be repeated.

If the Study 124 Day 1 Visit **does not coincide** with the Study 122B Safety Follow-up Visit, and if Study 124 Day 1 is ≤9 days after the Study 122B Safety Follow-up Visit, the Study 124 Day 1 assessments do not need to be repeated. If Study 124 Day 1 is >9 days after the Study 122B Safety Follow-up Visit, the subject will complete all Study 124 Day 1 assessments (except the OE if it was performed ≤12 weeks before the Study 124 Day 1 Visit).

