- IRT: Trypsin and trypsinogen are proteins produced by the pancreas that can be detected in the blood via the IRT assay. Evaluation of IRT is used in clinical practice as the basis of newborn screening for CF, wherein elevated levels at birth are associated with disease. Over time, however, patients with CF show a longitudinal decline in IRT with nondetectable levels observed around 5 years of age, indicating a loss of pancreatic function. Blood samples for IRT testing will be collected at multiple time points to evaluate potential changes in exocrine pancreatic function.

**Markers of Intestinal Inflammation:** Fecal samples will be collected to investigate biomarkers related to intestinal inflammation in CF patients, including but not limited to fecal calprotectin. Fecal calprotectin has been shown to be increased in pediatric patients with CF.  These data

support the concept that intestinal inflammation is a feature of CF and that intestinal inflammation can be monitored by measuring non-invasive biomarkers such as fecal calprotectin in clinical studies with CF patients.

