#### 12.3.1 General Considerations

All individual subject data will be presented in data listings based on the 124 All Subjects Set.

Continuous variables will be summarized using the following descriptive summary statistics: number of subjects, mean, SD, SE, median, minimum value (min), and maximum value (max).

Categorical variables will be summarized using counts and percentages.

**Baseline value** will be defined as the most recent non-missing measurement (scheduled or unscheduled) collected on or before the first dose of LUM/IVA in Study 124.

For sweat chloride, values at each visit will be based on averaged measurements from left and right arms as specified in Section 11.2.1. For Rollover Subjects, baseline will be defined as the most recent non-missing measurement (scheduled or unscheduled) collected on or before the first dose of LUM/IVA in Study 124. For LUM/IVA-naïve Subjects, baseline will be defined as the average of the values at screening and the pretreatment measurement on Day 1 of Study 124. If only 1 pre-first dose measurement of sweat chloride is available, that measurement will be considered the baseline.

Change (Absolute Change) from baseline will be calculated as postbaseline value – baseline value.

**Current Study Period** starts from the first dose of study drug in Study 124 to the last day in Study 124.

The Treatment-emergent (TE) Period for the Current Study Period starts on or after the first dose date of study drug in Study 124 to 14 days (inclusive) after the last dose of study drug in Study 124 or up to the last day in Study 124, whichever occurs first.

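### Change-from-baseline summaries pool LUM/IVA-naïve and Rollover Subjects, whose Study 124 baselines differ by a nominal 24 weeks of prior treatment, with no by-cohort display

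*SAP*

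**What the plan says.** **Baseline.** SAP 10.1 uses the "most recent non-missing measurement (scheduled or unscheduled) collected on or before the first dose of LUM/IVA in Study 124". Sweat chloride has its own rule. Naïve subjects get the average of the screening and pretreatment Day 1 values. Rollover Subjects keep the last-value rule, as in Protocol 12.3.1: "For Rollover Subjects, baseline will be defined as the most recent non-missing measurement (scheduled or unscheduled) collected on or before the first dose".

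**Who the cohorts are.** A Rollover Subject must have "Completed the 24-week Treatment Period and the Safety Follow-up Visit in Study 122B" (Protocol 8.1.1). Interruptions are allowed, so 24 weeks is nominal. For the naïve cohort, Protocol 8.2.1 states: "Subjects (male and female) will be 12 to <24 months of age on Day 1". Protocol 8.2.2 excludes "Ongoing or prior participation in an investigational drug study (including studies investigating LUM and/or IVA) within 30 days of screening". The naïve baseline is thus off-drug and before Study 124 treatment, although the criterion does not guarantee that a subject was never exposed.

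**Timing of Rollover Day 1.** Protocol 9.1 states: "For Rollover Subjects, the Day 1 Visit should be the same day as the Safety Follow-up Visit in Study 122B". If Day 1 falls no more than 9 days after that visit, "the Study 124 Day 1 assessments do not need to be repeated".

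**Analysis.** Protocol 12.3.3 and 12.3.4 ask for overall summaries on the Full Analysis Set. SAP 10.4 and 10.5 give tables by visit, plots of mean change with 95% CI, and an FE-1 shift table at 200 mg/kg, with no split by cohort. The lists in SAP 10.2.1 and 10.2.2 contain no cohort category, and the age they report is age at treatment initiation. The SAP separates the cohorts for the sweat chloride baseline and for visit windows (Appendix A), but in no planned summary.

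**The concern.** Within one table row, change means two things: change from an off-drug, pre-treatment value for naïve subjects, and change since Study 124 entry for subjects already treated in Study 122B. The secondary objective concerns the pharmacodynamics of long-term treatment in children defined by age at treatment initiation, so a reader will tend to take the pooled mean as change since treatment began. For Rollover Subjects it is not that.

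The plots add a second difficulty. The early points on several lines contain naïve subjects only and the later points contain both cohorts, so a line can move because its population changes. Descriptive tables and plots are the only planned summaries of these endpoints, so what needs protecting is that they can be read correctly.

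**Working it through.** **Inputs from the documents.** 24 weeks of treatment in Study 122B and 96 in Study 124 (SAP 7.1); about 50 subjects in all, with no split by cohort (SAP 7.2); visit windows (SAP Appendix A); 1 month = 30.4375 days (SAP Appendix G).

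**Assumed, not in the documents.** Rollover share p; fraction r of the treatment effect still present at Rollover baseline; a common full effect D in both cohorts; equal within-cohort SD; all 50 subjects contributing.

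**1. Cumulative treatment.** 24 + 96 = 120 weeks, which agrees with SAP 7.1. At the same nominal visit a Rollover Subject has a nominal 24 more weeks: 24 against 48 at Week 24, 48 against 72 at Week 48, and 96 against 120 at Week 96.

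**2. Age.** 168 / 30.4375 = 5.5 months. Rollover Subjects who started Study 122B at 12 to <24 months are nominally 17.5 to <29.5 months old at Study 124 Day 1, plus any off-drug gap, against 12 to <24 for naïve subjects. The ranges overlap, so the difference is one of averages.

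**3. Who is in each plotted point (SAP Tables 11-1 and 11-2).**

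| Endpoint | Naïve-only visits | First visit with both cohorts |
|---|---|---|
| Sweat chloride, fecal markers | Weeks 4, 12 | Week 24 |
| Growth | Weeks 4, 8, 16 | Day 15 (cohorts then alternate until Week 24) |
| IRT | Week 4 | Week 12 |

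**4. Dilution, sweat chloride only.** Naïve change = D and Rollover change = D(1 − r), so pooled change = (1 − p)D + pD(1 − r) = D(1 − p×r). Loss relative to D, p×r:

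| p | r = 0 | r = 0.1 | r = 0.25 | r = 0.5 | r = 1 (bound) |
|---|---|---|---|---|---|
| 0.2 | 0% | 2% | 5% | 10% | 20% |
| 0.4 | 0% | 4% | 10% | 20% | 40% |
| 0.6 | 0% | 6% | 15% | 30% | 60% |
| 0.8 | 0% | 8% | 20% | 40% | 80% |

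**5. Would the step on the sweat chloride plot show?** With constant true effects, the line moves from D at Week 12 (naïve only) to D(1 − p×r) at Week 24. With x = r×D/SD, the step is p×x in SD units. The Week 12 half-width is 1.96/√(50(1 − p)). The Week 24 half-width is 1.96×√((1 + p(1 − p)x²)/50).

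| p | Naïve n | Week 12 half-width (SD) | x at which step exceeds Week 12 half-width | x at which step exceeds Week 24 half-width |
|---|---|---|---|---|
| 0.2 | 40 | 0.31 | 1.55 | 1.67 |
| 0.4 | 30 | 0.36 | 0.89 | 0.74 |
| 0.6 | 20 | 0.44 | 0.73 | 0.47 |
| 0.8 | 10 | 0.62 | 0.77 | 0.35 |

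The step clears both intervals only above x = 1.67, 0.89, 0.73 and 0.77 respectively. This compares the step with each interval on the page. It does not test the difference, since the two means share the naïve subjects.

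**6. FE-1 shift table, illustration.** Take N = 50, p = 0.6 and an assumed 20% of subjects truly crossing 200 mg/kg, so 10 subjects: 20×0.2 = 4 naïve and 30×0.2 = 6 Rollover. If 0%, 50% or 100% of the Rollover crossings happened in Study 122B and lasted, the table counts 4 + 6 = 10, 4 + 3 = 7 or 4 + 0 = 4.

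**The case against.** Much of the opposing case stands.

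- **Carry-over is not shown.** Rollover Subjects enter at or after a safety follow-up visit, which favours an off-drug sweat chloride baseline. At r = 0 there is no dilution. The interval since the last Study 122B dose is not stated.
- **The plan is open and consistent.** Baseline is plainly defined, the protocol asks for overall summaries and the SAP follows it. Nothing contradicts itself.
- **Partial clues exist.** The n at naïve-only visits roughly reveals the split, the number with FE-1 below 200 mg/kg at baseline is shown, and all subject data are listed. None of these gives a mean or interval by cohort.

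A reader might infer more than the documents support:

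- *The pooled mean understates the effect on every endpoint.* The formula covers sweat chloride only. The protocol says that "patients with CF show a longitudinal decline in IRT", so age and time since initiation matter for IRT, but the sign of a cohort difference is not established for IRT, growth or calprotectin.
- *Rollover baselines are on-treatment values.* The last-value rule could reach back to one if a later result is missing or, for sweat chloride, the sample volume is below 15 µL (SAP 10.4.1). Whether it does depends on Study 122B schedules and data that are not given here.
- *The change from length to height at 730 days distorts growth z-scores.* SAP Appendix G applies a 0.7 cm correction, the age-based z-scores already adjust for age, and naïve subjects also pass that age during 96 weeks.

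**Conclusion.** The point holds as one of interpretation. It is certain from the documents that the pooled summaries join two baselines separated by a nominal 24 weeks of treatment, that the same visit mixes cumulative treatment times, that naïve-only visits feed the same plots, and that no by-cohort summary is planned.

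The consequence is conditional. If some Study 122B effect persists, the pooled sweat chloride change is diluted by p×r relative to change from pre-treatment, and the FE-1 shift table misses crossings made in Study 122B. Both sizes rest on assumed values, and the sweat chloride formula also on an equal effect in both cohorts. For growth, IRT and calprotectin, all that can be said is that the cohorts may differ.

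A reader might conclude that the analysis is invalid. It is not: the endpoints are secondary and exploratory, and SAP 10.1 plans no hypothesis test. This is a minor improvement, worth making because it costs little.

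**What to change.** Keep the Study 124 baseline and the overall summary that the protocol specifies.

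1. In SAP 10.4 and 10.5, add Rollover and LUM/IVA-naïve columns and plot series to the change-from-baseline summaries, and split the FE-1 shift table the same way.
2. Label the Rollover change as 'since Study 124 entry', and flag any Rollover baseline taken while on Study 122B treatment.
3. In SAP 10.2, report the number of subjects and the age at Study 124 Day 1 by cohort.
4. Optionally, and only if comparable Study 122B pre-treatment values exist, add a Rollover summary of change from the last value before the first Study 122B dose, by cumulative treatment time.

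**Cost.** Items 1 to 3 need SAP wording and extra columns and series, with no new visits. The price is precision: the 95% half-width 1.96/√n is about 0.39 SD at n = 25 and 0.62 SD at n = 10, against 0.28 SD at n = 50. Item 4 needs a merge with Study 122B data, whose comparability these documents do not show.
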